"LET'S TALK ABOUT COLLEGE STUDENT SLEEP: AN
INNOVATIVE NON-INVASIVE NEUROMODULATION
TREATMENT TO IMPROVE SLEEP QUALITY AND
ACADEMIC PERFORMANCE: RANDOMIZED
CLINICAL TRIAL" (USLEEP)

ID: USLEEP

[NCT ID not yet assigned] 15/11/2021

TITLE OF THE PROJECT

"Let's talk about sleep in college student: an innovative treatment based on non-invasive neuromodulation to enhance the sleep quality and academic efficiency: Randomized controlled trial" (USLEEP)

CENTERS AND RESEARCHERS:

- Dra. [name] (IP. Physiotherapist. PhD. University of Las Palmas de Gran Canaria).
- [name] [name] (Physiotherapist. University of Las Palmas de Gran Canaria).
- [name] (Physiotherapist. PhD. Alfonso X el Sabio University)
- [name] (Physiotherapist. PhD. Pontifical University of Salamanca).
- Dra. [name] (Biologist. PAD, PhD. Pontifical University of Salamanca)
- Dra. [name] (Physiotherapist. PhD. Pontifical University of Salamanca)
- [name] (Physiotherapist. PT, PhD. University of Alcalá de Henares)

ABSTRACT

Currently, disorders such as insomnia, narcolepsy or circadian rhythm disturbances are the most common among college students. The concern about the quality of sleep of university students, future professionals of the world, must be crucial for the scientific community, as well as for university professors and professors. Innovative electrotherapy technologies such as non-invasive neuromodulation NESA are showing effects on improving sleep quality, concentration and stress, so the objective of this project is to carry out a triple-blind randomized clinical trial with first-year science students from three universities. The design was made up of an intervention group with NESA technology and another control group in each of the centers. Where the quality of sleep will be analyzed,

This multicenter project hopes to demonstrate that non-invasive NESA neuromodulation can be a preventive treatment for the maintenance of sleep quality during stressful periods such as university exams, as well as being able to modulate perceived stress and translate into an improvement in student performance.

STUDY JUSTIFICATION:

INTRODUCTION:

The university student population has never been considered as possible affected by sleep problems. However, they are very susceptible to sleep disorders due to their pace of life, exams and their social life. Students also have a tendency to use exciting substances such as caffeine, tobacco, or heavy alcohol consumption. Consequently, sleep disorders that are closely related to academic performance can be generated. Identifying the most common and prevalent disorders in this population, as well as studying the most effective possible treatments should be one of the objectives of today's sleep medicine professionals. Currently, disorders such as insomnia, narcolepsy or circadian rhythm disturbances are the most common among college students. The concern about the quality of sleep of university students, future professionals of the world, must be crucial for the scientific community, as well as for university professors and professors (Al Salmani et al., 2020).

Fortunately, new emerging technologies such as non-invasive neuromodulation NESA, manage to neuromodulate the autonomic nervous system through electrotherapy and this has shown positive changes in the quality of sleep (Medina-Ramírez et al., 2021) and performance in young athletes, which can be extrapolated to young students who also require performance for their studies.

It is for this reason that with this study we want to deepen the responses generated by students to stimuli and stress generated throughout an exam period.

NESA NEUROMODULATION NON-INVASIVE TECHNOLOGY.

Non-invasive neuromodulation NESA was invented in Japan in 1989 by [name] et Al and their team at the Odawara Neurological Hospital, with the aim of improving the functionality of electrotherapy in the nervous system.

Currently its main quality is that its main therapeutic quality is based on its pleasant nature for the patient, in addition to being a non-invasive procedure it is used in various Hospitals, clinics and football clubs in Spain and the United Arab Emirates. The central manufacturing plant is based in the Basque Country, Spain, directed by the son of [name].

The objective of the NESA microcurrents generated by the X SIGNAL® device is none other than to introduce, by means of a non-invasive technique, electrical energy to normalize the nervous stimulus. This makes it an excellent complementary treatment to the activity of the doctor or physiotherapist. (Medina-Ramírez et al., 2021).

Its effects are achieved by establishing various input nerve pathways corresponding to the body dermis, through which the signals are intellectualized in time-space. These signals are the basis for achieving a normalization of the nerve impulse through microcurrents. Although the information transmittable through this force has a limit, rationalizing the signal creates a possibility to modulate the nervous system.

Noninvasive neuromodulation NESA occupies an independent position separate from classical electrotherapy. In this sense, it will act against any affection that causes excitement and tension in the cerebral nervous systems, osteoarticular muscular, and visceral vascular.

In this sense, sleep takes on special importance, the workhorse of any physical therapy.

Non-invasive neuromodulation NESA proposes a methodology with which it is possible to significantly reduce the biological energy costs of treatment with an electrical current supply. If several input routes of the stimulus are ensured, the intensity of the input energy can be reduced to levels typical of the physiological environment, allowing treatments that involve the whole organism.

If we also manage to translate the input pulse of each sensory stimulation into information in the form of data with polar, temporal and spatial properties, it can interfere more significantly in the transmission and processing of information from the central nervous system and, therefore, consequently, intervene in the possible existing anomalies. The condition for obtaining effects is not the intensity, but the informational nature of the medium that is introduced and the input method of said medium.

Conventional analog-type electrical stimulation treatments subject the human body to an excessively inefficient energy output compared to the information processing system deployed by the body itself.

The NESA X SIGNAL[®] device is a bioelectrical interface designed to enter, by affinity, in contact with the body, and bind to it through a series of "signals" previously converted into information. Starting from this premise, non-invasive neuromodulation NESA proposes the foundation of the science of electrophysiological information, that is, a procedure designed to calm and stabilize the excess activity of all related systems.

In many diseases, the central nervous system is subjected to excess activity of an interactive nature (eg, with the sympathetic nervous system or its reticular formation). There are a few effective treatment methods that inhibit excess activity without resorting to intense stimulation. This allows them not to cause pain or any other unpleasant effect, such as secondary or some type of dependency. By supplying imperceptible electrical signals, NESA microcurrents deepen the development of an original methodology that calms and stabilizes excess activity from all related systems. This process will be called normalized topographic stimulation generated by the NESA X SIGNAL[®], basic conditions for an energy of weak intensity to be effective.

Figure 1. Example of NESASIGNAL stimulation (NESASIGNAL DRIVE).

Therefore, the NESASIGNAL® is a treatment system for the supply of electrical current, which converts information, temporally and spatially, and controls it automatically, modulating the processing and transmission of information carried out by the human body.

NESASIGNAL technology also acts on this parameter, including a coordinated stimulation through 24 electrodes, modulating the nervous system through low-frequency bioelectric signals. The action on the different areas of the body is carried out through the current that circulates between them. Since each person has different conductivity and frequencies, and these can vary depending on multiple factors (age, physical constitution, sweating, etc.) there are different programs (transmission protocol of the impulse sequences) and disposition of the electrode mass. that address these situations.

The system is minimally invasive; superficial application, with electrodes connected by cable in gloves and anklets (or adaptations to amputated limbs), with 24 electrical access points. The characteristics of the current model are:

1. Emit low frequency pulses from 1.3 Hz to 14.28 Hz oscillating.
 1. Pulse emission at an intensity of 0.5 milliamps with a potential difference of ± 3 V and ± 6 V.
 2. Emission of impulses in a coordinated manner between 24 electrodes (6 electrodes per limb) that are stimulated simultaneously. 6 electrodes per limb are placed at different points of the peripheral nerve with lower impedance.
 3. Focusing of the impulses to a ground electrode, with the function of conductive wire.
 4. Stochastic algorithm emission in each pulse emission cycle. The signals are programmed in time and space.

To obtain the different therapeutic effects, the combination of up to 9 different programs is assigned. The electrical stimulation between the points follows a certain order, stimulus time and polarity change, generated automatically by means of a patented algorithm.

The impact of this ultra-weak electrical signal, practically imperceptible, is amplified thanks to its input through multiple routes and the phenomenon of stochastic resonance, configuring a circuit that encompasses the nervous system with related physiological functions. Has shown in preliminary studies, effects on improving concentration (Rico & Aranguren, 2016, 2017) neuralgic pain (Molina et al., 2020) and sleep quality (Contreras & Medina-Ramírez, 2021; Lledó-Amat et al., 2021)

NXSIGNAL® DEVICE COMPONENTS

[figure not shown]
The device consists of the following elements:

- Control console and device management. It consists of the connections for the cables to the electrodes, battery and configuration panel (Figure 2).

Figure 2. NXSIGNAL® Device Console

- Gloves for both hands and anklets for the feet. They incorporate fixed electrodes, connected by cable to the control console, positioned at the points of least resistance and greater connectivity with the peripheral nerves (Figure 3).

[figure not shown]
ZONA	COLOR	NERVIO
TOBILLERA 	ROJO	N. Peroneo superficial
	NEGRO	N. Safeno
	AZUL	N. sensitivo Sural
	AMARILLO	N. Tibial y ramas calcáneas
	BLANCO	N. Peroneo (rama superficial)
	VERDE	N. Peroneo profundo
GUANTE 	ROJO	N. Radial (rama anterior)
	NEGRO	N. Radial (rama posterior)
	AZUL	N. Cubital (rama anterior)
	AMARILLO	N. Cubital (rama cutánea dorsal)
	BLANCO	N. Mediano (rama cutánea palmar)
	VERDE	N. Cubital (rama dorsal)

Figure 3. Location of the electrodes according to the corresponding anatomical region (upper and lower image).

OBJECTIVES OF THE STUDY:

MAIN GOAL:

- To analyze the effects on the quality of sleep and student performance through the application of non-invasive neuromodulation NESA.

SECONDARY OBJECTIVES:

- Analyze if there is a correlation in the improvement of stress perception.
- To assess the influence between non-invasive neuromodulation and academic performance.

METHODOLOGY:

DESIGN:

Randomized clinical trial with passive control, triple blind (for the patient, the physiotherapist applying the technique and evaluator), with a parallel and multicenter design. The study will have two arms, the intervention group will undergo neuromodulation treatment with the NESA XSIGNAL® device and the control group will not carry out any intervention, but both will be evaluated for the same variables at the same times.

SCOPE AND STUDY POPULATION:

Multicenter study whose collaborating entities correspond to the University of Las Palmas de Gran Canaria, Alfonso X el Sabio University, the Pontifical University of Salamanca and the University of Alcalá de Henares. The study population will be students from the collaborating universities, corresponding to first-year health sciences degrees. For the selection of the sample, a non-probabilistic convenience sampling will be carried out, which allows selecting those accessible cases that agree to be included.

CALCULATION OF THE SAMPLE:

The present study is proposed as a pilot study due to the absence of similar studies in this field that allow a

calculation of the adjusted sample size. For this, 80 participants will be included, who must meet the established selection criteria.

CRITERIA FOR SELECTING THE PARTICIPANTS

INCLUSION CRITERIA.

- Healthy people
- Be enrolled in a degree in health sciences at the partner universities in the study in the first year.
- Optimal cognitive abilities and mentally competent to participate in the study.
- In cognitive conditions to complete the study questionnaires
- Have an optimal command of the Spanish language to complete the questionnaires.
- Signing of the informed consent for participation

EXCLUSION CRITERIA.

- Present some of the contraindications for a treatment with NESA X SIGNAL®: Pacemaker or other electrical surgical device, internal bleeding, do not apply electrodes on skin in poor condition, with ulcerations or wounds, acute febrile processes, pregnancy, acute thrombophlebitis and / or phobia of electricity, and pregnant.
- Combine another pharmacological treatment that influences the variables to be evaluated during the study.

ELIMINATION CRITERIA.

- Missing an intervention session of the 10 scheduled sessions.

RECRUITMENT OF PARTICIPANTS AND EVALUATION PROCESS.

Phase 1. Dissemination of the study

The dissemination of the participation of the subjects in the study will consist of making an initial contact through the teachers responsible for each center. Once informed, the students will receive an email with the complete information sheet containing the description of the study, the objective, the justification, the risks and benefits derived from participation, everything related to the protection of their personal data and the way of contacting the researcher in charge of each center (ANNEX 01). In the same actions, the established selection criteria will be reported.

Phase 2. Call for anamnesis of those interested in participating in the study and selection of study subjects.

Phase 3. Acceptance of participation in the study by signing the informed consent (ANNEX 02)

Once the consent is signed, the participant will fill in the participant's demographic characteristics questionnaire (ANNEX 03) and measures of baseline variables.

Next, the participant will be summoned to the laboratory of the corresponding university for the application of the evaluation intervention within the corresponding deadlines and indicated in the information sheet of the study.

RANDOM ASSIGNMENT:

Patients who agree to participate will be randomly assigned to one of the 2 arms of the study (real device or control), using a fixed-size block design generated by the data manager to guarantee balanced randomization for each of the arms and in each of the participating universities. The assignment process will be carried out hidden and will be carried out by the support researcher in the Unit indicated for this study. Each research subject will be assigned an identification code corresponding to correlative numbers from 1 to 80, with 1-20 subjects from the UPSA, from 21-40 students from the Alfonso X el Sabio University, from 41 to 60 students from the University of Las Palmas and from 61 to 80 from the University of Alcalá.

BLINDING:

The intervention to which the subjects have been assigned, the specialist and the researcher who collects the information and performs the follow-ups will be blinded. Data analysis will also be performed in a blinded fashion.

INTERVENTION PROTOCOLS

For neuromodulation:

Group 1: Application of Nesa microcurrents through the NXSIGNAL® generator twice a week.

The volunteer subjects of the study are treated with the NXSIGNAL® device in sessions of 60 minutes, twice a week and for 5 weeks (10 sessions).

The correct application of the NXSIGNAL® device, as well as an adequate programming, is of vital importance for the fulfillment of the objective. General guidelines will be established, which must always be followed with the application of NESA microcurrents, and specific guidelines for this particular study, in order to obtain a sample as homogeneous as possible and bring the programming of the device closer to the objective to be pursued. in the clinical trial. General guidelines for the application of NXSIGNAL®.

- The skin must be clean, free of creams and grease, so it will be necessary to clean with alcohol or similar. The device's gloves and socks will be placed in accordance with the established protocols, paying attention to the location of each semi-electrode in its anatomical position. The device has a color system to determine the location of each cable.
- The directing electrode will be located with the skin equally clean, and will be essential for the operation of the technology.
- The use of electronic devices by the patient, less than one meter away, is contraindicated in order to optimize their use. The electrodes are connected to the control console and the targeting electrode located on the intervertebral area between C7 and T1 (cervical area) and will follow the central treatment pattern with the following combination:

Programación X-Signal Estudio Calidad Sueño en Estudiantes

[figure not shown]

Figure 4. The numbers located vertically to the left of the image represent the number of sessions. The central blocks refer to the programs and the application time and in the vertical right column the type of central application of the targeting electrode is defined, located in the cervical area C7.

The default schedule is based on the goals set in this study. The main objective is to improve the quality of sleep. The secondary objectives are to correlate with improving perception of stress and academic performance.

Group 2: Control group without NESASIGNAL[®] application

The same protocol for the analysis of variables is followed, but without performing any type of treatment with the NESASIGNAL device.

DEFINITION OF THE STUDY VARIABLES AND MEASUREMENT INDICATORS:

The variables will be measured before the start of the intervention (PRE), at the end of the intervention (POST) and one month after the end of the study.

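### The trial is called triple-blind, but controls have no sessions and no sham, so students and therapists cannot be blinded and questionnaire differences cannot be credited to the current

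*Combined protocol and SAP*

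**What the plan says.** The Abstract plans to "carry out a triple-blind randomized clinical trial with first-year science students from three universities" without saying who is blinded. The Design section names three parties: "Randomized clinical trial with passive control, triple blind (for the patient, the physiotherapist applying the technique and evaluator"). Its next sentence defines the arms and says that "the control group will not carry out any intervention, but both will be evaluated for the same variables at the same times".

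The Blinding section adds that "the specialist and the researcher who collects the information and performs the follow-ups will be blinded" and that the data will also be analysed blind. It gives no method for achieving this.

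Under Intervention Protocols, Group 1 is treated "in sessions of 60 minutes, twice a week and for 5 weeks (10 sessions"), with gloves, socks and electrodes fitted. Group 2 follows the same assessments "without performing any type of treatment with the NESASIGNAL device". The elimination criterion is "Missing an intervention session of the 10 scheduled sessions".

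As for the aim, the Abstract "hopes to demonstrate that non-invasive NESA neuromodulation can be a preventive treatment for the maintenance of sleep quality" during stressful periods such as exams. Sleep quality is measured with the Pittsburgh questionnaire. The text under Academic Performance says that participants receive the questionnaires by email link and complete them electronically, with no contact with the researcher.

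**The concern.** Blinding is a statement about how well the result is protected from bias, and readers will rely on it most when the outcome is subjective. Here sleep quality, academic stress and coping are all rated by the participant. If the participant knows the allocation, expectation can affect the answers directly, and a blinded evaluator is not involved in the rating.

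The arms also differ in more than the current. One arm has scheduled sessions, contact with a physiotherapist and time during which electronic devices must be kept at least a metre away; the other has none of these. A difference on the questionnaires would combine any effect of the current with expectation, contact and session conditions. The Abstract's hope of showing that the neuromodulation can preserve sleep quality would then rest on a comparison that cannot isolate it.

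**Working it through.** **Step 1. Test each claimed blind against the arm definitions.**

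| Party | Claim | What the design does | Feasible? |
|---|---|---|---|
| Participant | Blinded (Design) | Attends ten fitted-device sessions, or none | No |
| Treating physiotherapist | Blinded (Design, Blinding) | Applies the device to Group 1 only; Group 2 has no session | No |
| Evaluator | Blinded (Design, Blinding) | Can be kept unaware if separate from treatment | Yes |
| Data analyst | Blinded (Blinding) | Can work with coded arms | Yes |

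The protocol describes the current as practically imperceptible. That would help only if both arms wore the device.

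**Step 2. Identify who rates each outcome.**

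- Pittsburgh, CEAU and A-CEA: the student, online. Evaluator blinding gives no protection.
- Salivary cortisol and first-semester average grade: not self-reported, so less open to reporting bias. Expectation or attention could still affect them, and without a sham they cannot separate the current from the session either.

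**Step 3. Compare contact time.** Active arm: 10 sessions × 60 min = 600 min = 10 hours. Control arm: 0 hours.

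**Step 4. Illustrate the consequence.** The plan has no figure to reproduce: the 80 participants are a pilot number with no effect size, SD or power behind it. It agrees with the identification-code ranges, 4 universities × 20 = 80.

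Inputs from the documents:
- 80 participants with balanced allocation, read as 40 per arm
- independent t-test, significance level 0.05

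Assumptions:
- a two-sided test (the plan does not say)
- no effect of the current
- a non-specific shift of d standard deviations in the self-reported score

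The rejection probability comes from the non-central t distribution with df = n1 + n2 − 2 and non-centrality d × √(n1 n2 / (n1 + n2)). For 40 v 40 the multiplier is √(1600/80) = 4.472, df = 78, and the critical value is 1.991.

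| Assumed shift d (SD) | Non-centrality | Probability of p < 0.05 |
|---|---|---|
| 0 | 0 | 5.0% |
| 0.2 | 0.894 | 14.3% |
| 0.3 | 1.342 | 26.3% |
| 0.4 | 1.789 | 42.4% |
| 0.5 | 2.236 | 59.8% |

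The normal approximation gives 14.6%, 26.9%, 43.2% and 60.9% for the four non-zero shifts.

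**Step 5. Allow for the elimination rule.** Only students with scheduled sessions can miss one, so the rule can shrink only the treated arm. Assuming 4 treated students are lost (36 v 40), the figures are 13.8%, 25.2%, 40.5% and 57.5%. Assuming 8 are lost (32 v 40), they are 13.2%, 23.9%, 38.4% and 54.8%. The picture barely changes.

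**The case against.** The strongest reply is that a sham may have been intended. The Random Assignment section labels the active arm as the real device, the Design section says the physiotherapist is blinded, and the elimination rule is not restricted to one arm. Those words would fit a sham design. However, the Design section calls the control passive and says it has no intervention, the Group 2 description repeats this, and no inactive device or placebo session appears anywhere. The explicit arm definitions outweigh a label. If a sham does exist, those definitions are wrong, so the text needs correcting either way.

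A second reply is that a no-treatment control is a legitimate choice for a pilot, and that under a sessions-versus-nothing question a non-specific shift is a real difference, not a false positive. That is right. The percentages above mislead only if a significant result is read as evidence about the current.

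Three smaller points also stand. Only the Design section names all three blinded parties; the Abstract gives just the label, and the Blinding section does not clearly say that participants are blinded. The unequal-arm figures add little. Nothing in the documents shows that ten hours away from nearby electronics changes sleep scores, so that is a possible contributor only. None of this restores the participant or therapist blind.

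**Conclusion.** The concern holds and must be fixed. As written, two of the three stated blinds, participant and treating physiotherapist, are incompatible with the control arm. This follows from the text alone and needs no assumption. Evaluator and analyst blinding can stand.

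The trial can estimate the effect of NESA sessions, as a package, against no sessions. It cannot attribute a difference to the current, and the self-reported sleep, stress and coping results are also open to reporting bias. The size of that bias cannot be derived from the documents. Under assumed shifts of 0.2 to 0.5 SD, a significant questionnaire difference would arise about 14% to 60% of the time with an inert current and 40 students per arm.

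**What to change.** 1. **Abstract:** replace the triple-blind description with: randomised clinical trial with blinded evaluator and blinded data analysis.
2. **Design:** delete the triple-blind phrase and its parenthesis, and state that participants and treating physiotherapists are not blinded.
3. **Blinding:** replace the text with: *Participants and treating physiotherapists know the allocation. The researcher who collects data and saliva does not deliver sessions and is not told the allocation; the data analyst works with coded arms. The questionnaires are self-completed by unblinded participants.*
4. **Random Assignment:** rename the arms as NESA sessions and no sessions.
5. **Conclusions:** limit them, for every outcome, to NESA sessions versus no sessions, not a specific effect of the current. Say so explicitly for the Pittsburgh, CEAU and A-CEA results.

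If a sham procedure was in fact intended, the Design and Group 2 descriptions must be reconciled with that and the procedure described.

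**Cost.** No added participants, sessions or measurements. The evaluator must not deliver sessions. The Design section already lists evaluator and physiotherapist separately, but the documents do not say whether the four recorders in the QA section also treat. This must be stated, and if they do treat, staffing has to change. The information sheet may need matching wording. The remaining cost is a less favourable description of the design and a narrower conclusion.

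### The elimination rule removes students after randomisation for one missed session and, as written, can act only in the NESA arm

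*Combined protocol and SAP*

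**What the plan says.** Under Elimination Criteria, set apart from the inclusion and exclusion lists, the protocol gives a single item: "Missing an intervention session of the 10 scheduled sessions".

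The section on random assignment says that students who agree to take part are "randomly assigned to one of the 2 arms of the study (real device or control"), balanced by arm and university. The session schedule appears under Group 1 only: "twice a week and for 5 weeks (10 sessions"). For controls, the design section says "the control group will not carry out any intervention", and the Group 2 text says they follow the same assessments "without performing any type of treatment with the NESASIGNAL device". Outcomes are due before the intervention, "at the end of the intervention (POST) and one month after the end of the study".

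The statistical analysis plan compares the groups with an independent-samples t test, or Kruskal-Wallis if the data are not normal, at 0.05. It uses repeated measures ANOVA or Friedman's test across times. It defines no intention-to-treat or per-protocol set, no handling of missing outcomes, and no replacement of eliminated students.

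**The concern.** Randomisation makes the two arms comparable only as long as the students assigned are the students analysed. Here a student's place in the comparison depends on behaviour after assignment, and controls have no described session to miss. The rule is also strict, since one absence in ten is enough.

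The documents suggest that attendance may not be unrelated to outcome. The introduction says the study looks at stress over an exam period, and grades are an outcome. The side-effects section foresees a warning that sleep phases may, exceptionally, be slightly altered in the first two treatment sessions. Students who are stressed, sleeping badly or short of study time could plausibly be those who miss a session. On the other side, the academic recognition offered for taking part may keep attendance high.

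A difference in sleep quality, cortisol, stress or grades could then partly reflect who attended every session. The t test takes the groups as they stand and cannot separate this from an effect of NESA. The ANOVA is described as a comparison of times within a group, so it does not supply the randomised contrast either. If outcomes are not collected from eliminated students, no later reanalysis can restore them.

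**Working it through.** **Reproducing the plan's figures.** Sessions: 2 per week × 5 weeks = 10, as stated. Participants: 4 universities × 20 codes = 80, as stated. Balanced blocks imply 80 / 2 = 40 per arm; this is inferred, since the plan does not state it.

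**Assumptions.** The documents give no miss rate, no clustering of misses and no attendance-outcome correlation, so these are varied. The true effect is set to zero, tests are two-sided at 0.05 (sidedness is not stated), all 40 controls are kept, and no baseline adjustment is made.

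**Formulas.** Let p be the chance of missing a session.
- Share with perfect attendance, independent misses: k = (1 − p)^10.
- The same with misses clustered within students (beta-binomial, within-student correlation 0.2): k = product over j = 0 to 9 of (4(1 − p) + j) / (4 + j), where 4 = (1 − 0.2) / 0.2.
- Spurious difference in SD: ρ·φ(z)/k. Here ρ is the correlation of outcome with a latent attendance trait, z the (1 − k) normal quantile and φ the normal density.
- Type I error: noncentral t with 40k and 40 students.

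**Worked case, p = 5%, independent.** k = 0.95^10 = 0.599, so 40 × 0.599 = 23.9 students are kept. z = −0.25, φ(z) = 0.387 and φ(z)/k = 0.646. The bias is 0.2 × 0.646 = 0.129 SD, or 0.4 × 0.646 = 0.258 SD. The standard error is √(1/23.9 + 1/40) = 0.258 SD, so the noncentrality is 0.50 or 1.00 and the type I error 7.8% or 16.6%.

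| p | ρ | Independent: kept of 40, bias (SD), type I | Clustered: kept of 40, bias (SD), type I |
|---|---|---|---|
| 1% | 0.1 | 36.2, 0.019, 5.07% | 37.9, 0.011, 5.03% |
| 2% | 0.2 | 32.7, 0.065, 5.85% | 35.9, 0.040, 5.34% |
| 5% | 0.2 | 23.9, 0.129, 7.8% | 30.4, 0.082, 6.3% |
| 5% | 0.4 | 23.9, 0.258, 16.6% | 30.4, 0.163, 10.3% |
| 10% | 0.4 | 13.9, 0.424, 26.8% | 22.9, 0.274, 17.7% |

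Simulation with 200,000 trials per independent case gave rejection rates of 5.1, 5.8, 7.8, 16.7 and 26.8% for these rows. The sign of ρ sets the direction of the bias; the error rate is the same either way. The last row is an extreme case.

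**No correlation.** With ρ = 0 there is no bias, only lost data. The standard error relative to 40 v 40 is √((1/n + 1/40)/(2/40)) = 1.03, 1.05, 1.15 and 1.39 for n = 36, 33, 24 and 14.

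**The case against.** Five points can be made against this.

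1. **Elimination is not defined.** It could mean stopping sessions, leaving the study, or being replaced. Annexes 01 and 02, the information sheet and consent form, are not in the text available and might say more. This stands as a limit on certainty. However, nothing in the analysis plan counters the plain reading. Replacement would change the numbers retained but leave the selection in place.

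2. **Controls might have sham sessions.** The design is called "triple blind (for the patient, the physiotherapist applying the technique and evaluator"), and the phrase real device or control points the same way. If selection were equal in both arms, the bias would cancel and only data would be lost. But two explicit statements give controls no treatment. Even with sham sessions the rule would remain an exclusion after randomisation.

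3. **The bias is assumed, not shown.** This is correct. At miss rates of 1 to 2% and correlations of 0.1 to 0.2 it is negligible to small, and the documents do not say which region applies.

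4. **Baseline data could help.** PRE values and the university access grade are collected, and stable differences cancel in within-person change. The plan does not say whether POST values or changes are compared, and neither removes selection related to change during the trial.

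5. **It is a pilot.** "The present study is proposed as a pilot study due to the absence of similar studies in this field" lowers the stakes of type I error. The trial still tests group differences at 0.05, and its abstract hopes to demonstrate a preventive effect.

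**Conclusion.** The concern holds and must be fixed. The plan states a rule that acts after randomisation, in one arm only on its plain reading, and no analysis population offsets it. That conclusion rests on the text and not on the simulated error rates.

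The size is not known. Across the scenarios examined it runs from nothing of consequence (type I error 5.0 to 5.1% at 1% missed and correlation 0.1) to 18 to 27% in the extreme case of 10% missed and correlation 0.4. The direction could favour either arm. If attendance is unrelated to outcome, the harm is lost precision alone, a standard error about 3 to 39% larger with 36 down to 14 NESA students left. All of this assumes 40 per arm, no sham sessions, and elimination meaning removal from the analysis.

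**What to change.** 1. State that a missed session does not remove a student from follow-up or analysis. Whether further sessions are offered is for the sponsor to decide.
2. Make the primary analysis all randomised students in their assigned arm.
3. Seek POST and one-month questionnaires, salivary cortisol and the semester grade from everyone, whatever their attendance. Use all available measurements, and report missing outcomes by arm.
4. Report sessions attended, and keep attendance at all 10 only as a labelled per-protocol sensitivity analysis.

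The passages on blinding and on the control arm should also be reconciled, so that it is clear whether controls have sessions at all.

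**Cost.** About one paragraph of protocol and SAP text, plus follow-up of NESA students who miss a session. Under the scenarios above that is 40 − 37.9 = 2.1 to 40 − 13.9 = 26.1 students. At two time points this is roughly 4 to 52 questionnaire sets, and as many saliva samples if one is taken each time. The trial already planned to measure these students. There are two downsides: incomplete attendance will dilute the estimated effect somewhat, and students who missed a session must be asked back for saliva, which an emailed link cannot collect.
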